1 STUDY SYNOPSIS

Protocol No.: MOT-C-201	Study Drug: MOTREM (LR12)
Coordinating Investigator: [name] ; Inserm 1435 Clinical Investigational Center	
Title of the Study: Safety, Tolerability, Pharmacokinetics and Pharmacodynamics of 3 Doses of MOTREM in Patients with Septic Shock. A Randomised, Double-blind, Two-Stage, Placebo Controlled Study	
Study Centre(s): Multi-centre, multi-national study, refer to separate list in study file	
Study Period (planned): 
First patient first visit: Q2/2017Last patient last visit: Q2/2018	Development Phase: Clinical Phase IIa
Objectives: Primary 
To evaluate the safety and tolerability of MOTREM in patients with septic shock Secondary 
To evaluate the effects of MOTREM exposure over up to 5 days in patients with septic shockTo evaluate the PK/PD and dose/PD relationship to TREM-1 pathway related markersTo evaluate the effect of MOTREM on transcriptomicsTo evaluate the effect of MOTREM on clinical parameters (e.g. vasopressor doses, vasopressor-free days, ventilator-free days, mortality)	
Methodology This is a randomised, double-blind, two-stage, placebo controlled study. It consists of 2 stages with a similar treatment regimen, in which 0.3, 1.0 or 3.0 mg/kg/h of MOTREM is tested versus placebo. All patients with a diagnosis of septic shock will be considered for study participation. The applicable local requirements for informed consent will be followed. All potential study patients will undergo standard care management procedures. After screening for eligibility, patients will be randomised to one of the treatment arms. They will then either receive a 5 mg/kg loading dose of MOTREM over 15 minutes followed by a continuous i.v. infusion of MOTREM or a matching placebo on top of standard of care. Treatment with study drug must be initiated as early as possible, but no later than 24 hours after the onset of septic shock, defined by the start of vasopressor therapy. Blood samples for the determination of MOTREM (LR12) plasma concentrations and exploratory pharmacodynamic analyses will be collected before and throughout the treatment period. Patients will be treated until 12 (± 2) hours after the resolution of their septic shock (defined as vasopressor withdrawal) with a maximum treatment duration of 5 days (120 hours). The survival status of patients after 28 and 90 days will be collected. Stage 1 is investigating multiple ascending doses of MOTREM or placebo in a sequential design in cohorts of 4 patients (3:1 randomisation). After completion of a cohort (for up to 5 days of infusion), safety and PK data will be reviewed by an independent data safety monitoring board (DSMB) and the study will progress to the next cohort/stage.	
Study Flowchart Stage 1 
Per Cohort
 
Standard Care
 
New Diagnosis Sepic Shock
 
Screening/ Randomization
 
MOTREM (3 Pts.)
 
Placebo (1 Pt.)
 
Follow up
 
≤24 hours
 
Study drug infusion up to 5 days
 
10±1 days 28±2 days 90±2 days
	

Stage 2 investigates 3 doses of MOTREM in a randomised, balanced, parallel-group design involving up to 3 doses of MOTREM and a placebo arm. Only dose arms of MOTREM considered to be safe and well tolerated during Stage 1 will be administered in Stage 2.

Study Flowchart Stage 2

Number of Patients

The total planned number of patients is 48: twelve (12) patients in stage 1 and 36 patients in stage 2. The cohorts in stage 1 may be repeated according to the adaptive features of the study protocol. The total number of patients will not exceed 66 patients.

Diagnosis and Main Criteria for Inclusion

Diagnosis: Septic Shock (according to Sepsis-3)

Inclusion Criteria:

To be eligible for the study, patients must meet the following criteria:

1. Provide written informed consent (proxy/legal representative) according to local regulations
2. Age 18 to 80 years

Sepsis

3. Documented or suspected infection: lung, abdominal or elderly UTI (≥ 65 years)
4. Organ dysfunction defined as acute change in SOFA score ≥ 2 points

Shock

5. Refractory hypotension requiring vasopressors to maintain MAP ≥ 65 mm Hg despite adequate volume resuscitation of at least 20 ml/kg within 6 hours
6. Hyperlactatemia (blood lactate >2 mmol/L or 18 mg/dL). This criterion must be met at least once for the purpose of diagnosis within the 24 hours before study drug administration

Exclusion Criteria

The presence of any of the following will exclude a patient from study enrolment:

1. Previous episode of septic shock (vasopressor administration) within current hospital stay
2. Underlying concurrent immunodepression (specified in appendix 2)
3. Solid organ transplant requiring immunosuppressive therapy
4. Known pregnancy (positive serum pregnancy test)
5. Prolonged QT syndrome (QTc ≥ 440 ms)
6. Shock of any other cause, e.g. hypotension related to gastrointestinal bleeding
7. Ongoing documented or suspected endocarditis, history of prosthetic heart valves
8. End-stage neurological disease
9. End-stage cirrhosis (Child Pugh Class C)
10. Acute Physiology And Chronic Health Evaluation (APACHE) II score ≥ 34
11. End stage chronic renal disease requiring chronic dialysis
12. Home oxygen therapy on a regular basis for > 6 h/day
13. Severe obesity (BMI ≥ 40)
14. Recent CPR (within current hospital stay)
15. Moribund patients
16. Decision to limit full care taken before obtaining informed consent
17. Participation in another interventional study in the 3 months prior to randomisation
18. APACHE II score < 14

Test Product, Dose and Mode of Administration

MOTREM (LR12) will be administered as continuous i.v. infusion for up to 5 days. The doses administered are as follows:

Dose level T = 15'	i.v. loading dose	Maintenance i.v. dose
	[mg/kg]	[mg/kg/h]
Dose level 1	5.0	0.3
Dose level 2	5.0	1.0
Dose level 3	5.0	3.0

Reference Product, Dose and Mode of Administration

Matching placebo (saline without MOTREM)

Duration of Treatment

Study drug will be administered until 12 (± 2) hours after the resolution of shock (vasopressor cessation) for a maximum of five (5) days.

Duration of Clinical Study

Duration of i.v. infusion: up to 5 days

Duration of follow-up: up to 90 days

Criteria for Evaluation**Safety Parameters**

- Vital signs: systolic (SBP) and diastolic (DBP) blood pressure, heart rate, and body temperature (tympanic).
- ECG (12-lead ECG)
- Safety laboratory tests: haematology, coagulation, plasma biochemistry.
- Presence of anti-LR12 antibodies
- Adverse events: from screening until study completion.

Pharmacokinetics

Plasma concentrations of LR12 will be measured by a validated LC-MS/MS assay and analysed using a non-compartmental analysis to obtain estimates of the PK parameters

Pharmacodynamics (exploratory)

sTREM-1, immune and vascular related biomarkers

Clinical Parameters (exploratory)

- Resolution of organ dysfunction (SOFA score total and individual domains)
- Vasopressor use
- Invasive mechanical ventilation
- Renal support
- Time until shock reversal defined as cessation of vasopressor support for 24 hours
- Mortality at day 28 and at day 90

Statistical Methods**Descriptive Statistics**

Demographics, baseline characteristics, and disposition data will be summarised by treatment group (Placebo, Dose level 1, Dose level 2 and Dose level 3).

Safety, pharmacodynamic, pharmacokinetic and clinical data will be summarised by treatment group (Placebo, Dose level 1, Dose level 2 and Dose level 3), and over time.

Qualitative variables will be presented using the number of patients, the number of missing values, the frequency and the percentage per modality.

Quantitative variables will be reported using the number of patients, the number of missing values, the mean, the standard deviation, the median, the first and the third quartiles, the minimum and the maximum.

Geometric means and CV may be presented for variables with a skewed distribution.

Between groups comparisons are calculated using an independent t-test or ANOVA-test for quantitative variables with a parametric distribution, or Mann-Whitney-test or Kruskal Wallis-test for variables with a non-parametric distribution.

Cytokine distribution and vital signs over time are analysed by a repeated measures ANOVA (mixed models), if significant followed by the Bonferroni post-hoc test.

Data is tested for normality using Kolmogorov-Smirnov-test

HISTORY OF CHANGES

Changes from version 3.1 of the study protocol, dated 08 January 2018

- Introduction of retrospective data collection and exploratory post-hoc analysis of
 - Additional SOFA score data to replace data treated as missing in the original analysis
 - Duration of ICU stay
- Implementation of non-substantial change on plasma sample use documented on note to file dated 08 October 2018

Study protocol version 4.0 applies to study sites outside of France only

Changes from version 2.1 of the study protocol, dated 31 October 2017

- Addition of an interim analysis (section 15.4)
- Clarification of concomitant medication recording
- Minor corrections and clarifications

Study protocol version 3.0 dated 04 January 2017 applies to study sites outside of France only

Changes from version 1.3 of the study protocol, dated 12 September 2017

- Addition of blood samples for DNA analyses related to the TREM-1 signalling pathway
- Addition of a paragraph detailing the analysis and storage of blood samples
- Blood levels of sTLT-1 will not be analysed
- Name change of IMP management provider implemented
- Rating of Adverse Events updated for consistency with eCRF
- Minor corrections and clarifications

Study protocol version 2.0 dated 31 October 2017 applies to study sites outside of France only

Changes from version 1.2 of the study protocol, dated 29 August 2017

- Minor corrections and clarifications on the timing of blood samples in tables 1 and 2

These changes are **classified as non-substantial** by the sponsor according to the EU Clinical Trials Directive and section 8.2 of this study protocol.

Study protocol version 1.2, dated 29 August 2017 implemented the following changes from version 1.0 of the study protocol, dated 20 February 2017

- Changes requested by the French ANSM for sites in France:
 - Addition of exclusion criterion “APACHE II score <14”
 - Measurements of interferon- γ on days 1, 3, 5 and 28
 - Additional timepoint for the measurement of anti-drug antibodies on day 10
 - Direct antibody test (direct Coombs) at baseline (pre-dose), days 10 and 28
 - Addition of free bilirubin to the biochemistry laboratory parameters
 - Update of SUSAR reporting requirements for France
- Minor corrections and clarifications

Study protocol version 1.1 is only applicable to sites in the Netherlands

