8 INVESTIGATIONAL PLAN

8.1 Overall Study Design and Plan Description

This is a randomised, double-blind, two-stage, placebo controlled study. It consists of 2 stages with a similar treatment regimen, in which 0.3, 1.0 or 3.0 mg/kg/h of MOTREM is tested versus placebo.

All patients with a diagnosis of septic shock will be considered for study participation. The applicable local regulations and requirements for informed consent will be followed. All potential study patients will undergo standard care management procedures.

After screening for eligibility, patients will be randomised to one of the treatment arms. They will then either receive a 5 mg/kg loading dose of MOTREM over 15 minutes followed by a continuous i.v. infusion of MOTREM or a matching placebo on top of standard of care.

Treatment with study drug must be initiated as early as possible, but no later than 24 hours after the onset of septic shock, defined by the start of vasopressor therapy. Blood samples for the determination of LR12 plasma concentrations and exploratory pharmacodynamic analyses will be collected before and throughout the treatment period.

Patients will be treated until 12 (± 2) hours after the resolution of their septic shock (defined as vasopressor withdrawal) with a maximum treatment duration of 5 days (120 (± 2) hours).

The status of patients after 28 and 90 days will be collected.

Stage 1 is investigating multiple ascending doses of MOTREM or placebo in a sequential design in cohorts of 4 patients (3:1 randomisation). After completion of a cohort (for up to 5 days of infusion), safety and PK data (limited to PK data available) will be reviewed by an independent DSMB and the study will progress to the next cohort/stage.

A flowchart of the sequential dose levels in stage 1 is provided in Figure 1.

[figure not shown]

Figure 1: Flow Chart of sequential Dose Levels tested in Stage 1

A flowchart for stage 1 (per cohort) is provided in Figure 2.

[figure not shown]

Figure 2: Flow Chart Stage 1 (per cohort)

Stage 2 investigates 3 doses of MOTREM in a randomised parallel-group design. The treatment regimen for the patients is identical to stage 1. A flowchart for stage 1 is provided in Figure 3.

[figure not shown]

Figure 3: Flow Chart Stage 2

All assessments performed in the study are summarised in the study schedule provided in Table 1 and Table 2.

Table 1: Study Schedule

	Screen.	Treatment						Day 10	EoS	Follow-up
		≤24H	Day 0	Day 1	Day 2	Day 3	Day 4			

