11.3.2 Treatment Period (Day 1 to Day 4)

During the treatment period of up to 5 days, the following assessments will be performed daily (approximately at the same time of day):

- Concomitant therapy
- SOFA score
- Vital signs
- ECG
- Vasopressor use
- Invasive mechanical ventilation
- Intubation
- Mortality
- Adverse events
- Blood sample for ABG and P/F
- Blood samples for laboratory tests (according to schedule provided in Table 2):
 - Clinical Laboratory
 - Pharmacokinetics
 - Biomarkers
 - RNA profile
 - Plasma samples for retention (Day 1 only)
- Continued treatment with MOTREM i.v. (according to Table 5 or Table 6)

11.3.3 End of Infusion/Day 5

Patients will be treated until 12 (± 2) hours after the resolution of their septic shock (defined as vasopressor withdrawal) with a maximum treatment of 5 days (120 (± 2) hours). An

interruption of vasopressor treatment of up to 6 hours is permitted and not considered vasopressor withdrawal).

Patients may also be withdrawn from treatment for other reasons (see section 9.5).

At the end of treatment, the i.v. infusion will be stopped and the following assessments will be performed:

- Concomitant therapy
- SOFA score
- Vital signs
- Weight
- ECG
- Vasopressor use
- Invasive mechanical ventilation
- Intubation
- Mortality
- Adverse events
- Blood sample for ABG and P/F
- Blood samples for laboratory tests (according to schedule provided in Table 2):
 - Clinical Laboratory
 - pharmacokinetics
 - biomarkers
 - RNA profile

If the treatment is stopped any day before D5, the assessments listed above will be performed only once the day of the end of infusion.

For all patients alive, the SOFA score will however be calculated until day 5, no matter when the study treatment stopped. This data will be collected to the extent available in source data and analysed post-hoc (see section 15.5).

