12.8 Requirement of Vasopressor, Mechanical Ventilation and Intubation

The beginning and end of study of vasopressor therapy, invasive mechanical ventilation and intubation will be documented in the eCRF.

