12.10 Mortality Assessment

If a patient dies during the course of the study (time of informed consent to day 90 follow-up), the date and time of death will be documented. If possible, the cause of death will be documented.

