15.1 Statistical Methods

15.1.1 General Considerations

The analysis will be computed with SAS Version 9.4 (Copyright© 2013 by SAS Institute Inc., Cary, NC, USA).

Unless otherwise specified, baseline is defined as the last planned assessment prior to first dosing and no subgroup analysis is currently planned.

Missing safety, pharmacodynamic, pharmacokinetic and clinical data will not be replaced and will be treated as missing from summary and statistical analyses.

Unless otherwise specified, all treatment comparisons will be two-sided and significance will be assessed at the 5% level.

All safety, pharmacokinetic, pharmacodynamic and clinical data will be summarised by treatment group (Placebo, Dose level 1, Dose level 2 and Dose level 3), and visit, as appropriate.

Qualitative variables will be presented using the number of patients, the number of missing values, the frequency and the percentage per modality.

Quantitative variables will be reported using the number of patients, the number of missing values, the mean, the standard deviation, the median, the first and the third quartiles, the minimum and the maximum.

Between groups comparisons are calculated using an independent t-test or ANOVA-test for quantitative variables with a parametric distribution, or Mann-Whitney test or Kruskal Wallis-test for variables with a non-parametric distribution.

Data is tested for normality using Kolmogorov-Smirnov-test.

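### Shock reversal carries no survival condition and no rule for death or late limitation of care, so deaths can shorten or be hidden in the time to reversal

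*Combined protocol and SAP*

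**What the plan says.** The synopsis (Criteria for Evaluation, Clinical Parameters) and section 15.1.3 use the same words: "Time until shock reversal defined as cessation of vasopressor support for 24 hours". Neither place mentions survival, blood pressure without support, death on vasopressors or limitation of care, and neither gives the time origin.

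Related text:

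- The infusion rule in the synopsis and section 8.1 also treats vasopressor withdrawal as the end of shock: "resolution of their septic shock (defined as vasopressor withdrawal". Section 11.3.3 adds that an "interruption of vasopressor treatment of up to 6 hours is permitted and not considered vasopressor withdrawal". It says nothing about death or limitation of care.
- Section 12.8 on data capture: "The beginning and end of study of vasopressor therapy, invasive mechanical ventilation and intubation will be documented in the eCRF". No reason for stopping is named.
- Section 12.10: if a patient dies, "the date and time of death will be documented".
- Exclusion criterion 16 covers limitation of care only if it was decided earlier: "Decision to limit full care taken before obtaining informed consent". Later decisions are not addressed.
- Section 15.1.1: missing clinical data "will not be replaced and will be treated as missing from summary and statistical analyses".
- Section 15.1.5 describes clinical parameters by group and visit. It does not name time to shock reversal, censoring or competing events. Section 15.1.3 defers endpoint detail to a separate SAP, whose text is not among the documents supplied.

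**The concern.** Vasopressors end for three different reasons: the patient recovers, the patient dies, or support is withdrawn after a decision to limit care. The definition rests on the stop alone and so does not separate them. Elsewhere the protocol does make this distinction: section 11.3.3 limits the day-5 SOFA calculation to patients who are alive.

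This is the clinical parameter closest to the haemodynamic signal in section 6.3, where the drug reduced norepinephrine need in a mini-pig model. Sections 6.3 and 8.5.1 say the data will help design later studies, and section 15.4 says the unblinded 28-day analysis may inform business decisions. A reversal time that deaths can shorten, or from which they can disappear, is a poor basis for either use.

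**Working it through.** The plan gives no effect size, event count or expected time for this endpoint, so there is no stated figure to reproduce. The group sizes agree: 3×4 + 4×9 = 48, and 3 + 9 = 12 per group. The only mortality figure is almost 30% for severe sepsis (section 6.1), with no time frame. On 12 patients that is 0.30 × 12 = 3.6.

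**Step 1. Which patients meet the definition?**

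| Patient | Any stop counts | 24 observed hours off support needed |
|---|---|---|
| Weaned, alive 24 h later | event | event |
| Dies on vasopressors, or within 24 h of stopping | event | no event; handling not stated |
| Support limited after enrolment, survives at least 24 h | event | event |

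The third row holds on both readings. The second depends on the reading, and the documents do not choose one.

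**Step 2. Model A, competing constant hazards.** Assumptions, none from the documents: true median reversal m = 3 days (range 2 to 4), a share s dying on vasopressors, and no drug effect on reversal. Reversal hazard r = ln 2 / m; death hazard d = r·s/(1−s).

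- Every stop counts: median = ln 2/(r+d) = m(1−s).
- Deaths dropped as missing: time to reversal among those who reverse has the same distribution, so the median is again m(1−s).
- Deaths censored: median = m, whatever s is.
- Death as competing event: cumulative reversal by day 28 = [r/(r+d)]·[1−exp(−28(r+d))].

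For m = 3, r = 0.231 per day; s = 30% gives d = 0.099 and s = 50% gives d = 0.231.

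| Share dying on vasopressors | 15% | 30% | 50% |
|---|---|---|---|
| Every stop counts, or deaths dropped: median (days) | 2.55 | 2.10 | 1.50 |
| Deaths censored: median (days) | 3.0 | 3.0 | 3.0 |
| Competing event: median (days) | 3.3 | 3.8 | not reached |
| Competing event: reversed by day 28 | 85% | 70% | 50% |

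For m = 2 the first row is 1.7 / 1.4 / 1.0 days; for m = 4 it is 3.4 / 2.8 / 2.0 days. In 20,000 simulated trials with 12 per arm, m = 3 and 30% versus 50% deaths, the more lethal arm had the shorter median in 73% of runs if every stop counts, 68% if deaths are dropped, and 25% if death counts as no reversal.

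**Step 3. Model B, sensitivity to death timing.** Assumptions: survivors are weaned at a lognormal time (median 2.5 days, log-SD 0.7), and a share s (30% or 50%) dies on vasopressors at an exponential time. If every stop counts, the median t solves (1−s)·Φ(ln(t/2.5)/0.7) + s·(1−2^(−t/median death time)) = 0.5.

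| Median death time (days) | 1 | 2 | 2.5 | 3 | 4 |
|---|---|---|---|---|---|
| 30% die: median (days) | 2.05 | 2.39 | 2.50 | 2.59 | 2.74 |
| 50% die: median (days) | 1.73 | 2.30 | 2.50 | 2.68 | 2.97 |

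The more lethal arm looks faster only while deaths come earlier than recoveries. If deaths are dropped, both arms show 2.5 days and the difference disappears. Counting live recoveries only gives 70% versus 50% in every column.

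**Step 4. Limitation of care alone.** If deaths on support do not count, but an assumed 10% of deaths follow limitation of care with at least 24 h survival, the proportions become 0.70 + 0.1×0.30 = 73% and 0.50 + 0.1×0.50 = 55%. The direction is kept and the gap shrinks from 20 to 18 points.

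**The case against.** A reader might infer that every stop at death counts as reversal, that reversal therefore tends to 100% in every arm, and that a lethal dose will look faster. The documents do not support this. The 24-hour requirement can fairly be read as 24 observed hours off support, which a patient who dies sooner never completes. On that reading only limitation-of-care stops with later survival are misclassified, and Step 4 suggests a small effect. A competing-event analysis then handles deaths correctly, because death precedes completion of the 24 hours. Step 3 shows that the faster-looking lethal arm depends on early deaths. Moribund patients and those with an APACHE II score of 34 or more are excluded, so a 1-day median death time is a severe assumption. These objections stand.

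It is also fair that the endpoint is labelled exploratory in the synopsis and sits among the secondary endpoints in 15.1.3, that clinical analyses are descriptive, that mortality at days 28 and 90 is reported beside it, and that DSMB progression rests on AE, SAE and PK data. Excess deaths would be visible in the study as a whole. This limits the weight.

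Two objections do not remove the point. The separate SAP may settle the handling of deaths, but nothing in the supplied text does. And the observed-hours reading leaves patients who die without reversal with no rule except that for missing data, which can shorten the median (Model A) or hide the deaths (Model B).

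A reader might also infer a conflict between sections 8.1 and 11.3.3. There is none: both rest on vasopressor withdrawal.

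**Conclusion.** The concern holds as a gap in the definition. The text does not exclude a stop at death. On any reading it counts a stop after limitation of care followed by 24 hours of survival, and it gives deaths without reversal no place except as missing data. Time to reversal can then be shortened by deaths or can hide them.

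The size is illustrative. With 30% versus 50% dying on vasopressors, Model A gives 2.1 versus 1.5 days. Model B runs from 2.05 versus 1.73 days (median death at 1 day) to 2.74 versus 2.97 days (at 4 days). The death shares, death times and recovery times are all assumptions; the almost 30% in section 6.1 is overall mortality in severe sepsis, not death on vasopressors. What does not depend on death timing in these models is that counting death as no reversal puts the arms in the right order (70% versus 50%). The change is worth making, but it does not touch the primary safety objective.

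**What to change.** In the synopsis and section 15.1.3, define shock reversal as being alive and free of all vasopressors for 24 consecutive hours, timed from the start of infusion. Count death before those 24 hours are complete as no reversal: treat it as a competing event and report cumulative incidence of reversal by arm. The vasopressor stop times (12.8) and the date and time of death (12.10) are already collected, so this part needs no new field.

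For limitation of care, use the retrospective source-data route in section 15.5. Where records allow, abstract the reason for the vasopressor stop and the date and time of any post-enrolment limitation decision, class such stops as no reversal, and state how many patients have no recorded reason.

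This protocol version follows an original analysis, so present the result as a labelled re-analysis beside the original definition, with the rules fixed in the separate plan that section 15.5 foresees.

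Cost: one definition sentence, one added analysis and a small amount of source abstraction. Reported reversal rates will be lower, and the re-analysis is post hoc.

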15.1.3 Endpoints

Safety and tolerability will be the primary endpoint and it will be monitored during the course of the study as specified below:

Safety and Tolerability Parameters

- Vital signs: systolic (SBP) and diastolic (DBP) blood pressure, heart rate, and body temperature.
- ECG (12-lead ECG)
- Safety laboratory tests: haematology, coagulation, plasma biochemistry.
- Presence of anti-LR12 antibodies
- Adverse events: from screening until study completion.

Secondary endpoints include the following:

Pharmacokinetics

Plasma concentrations of LR12 will be measured by a validated LC-MS/MS assay and analysed using non-compartmental methods to obtain estimates of the PK parameters.

Pharmacodynamics (exploratory)

The concentration profiles of biomarkers (sTREM-1, immune and vascular related biomarkers) over time and biomarker mRNA levels will be analysed.

Clinical Parameters

- Resolution of organ dysfunction (SOFA score total and individual domains)
- Vasopressor use
- Invasive mechanical ventilation
- Renal support
- Time until shock reversal defined as cessation of vasopressor support for 24 hours
- Mortality at day 28 and day 90

Safety and tolerability will be the primary endpoint and in addition, the exposure of MOTREM will be analysed. The biomarker concentration profiles over time and the area under the concentration (AUC) curves will be analysed as secondary PD variables.

The MOTREM concentration profile over time and the main derived PK parameters will be analysed as PK endpoints.

The endpoints and their analysis will be further specified in the statistical analysis plan (SAP).

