15.1.5 Safety Analyses

Adverse events will be coded using the MedDRA dictionary version 18.1 or higher. Treatment emergent adverse events (events start after the first dose of investigational treatment or events present prior the administration of investigational treatment and worsened during the study (increased in severity)) will be classified by primary system organ class, preferred term and treatment group. Separate summaries will be performed for study medication related events, death, serious adverse events, adverse events leading to discontinuation of study medication and other adverse events of interest.

Other safety parameters that will be assessed include safety laboratory parameters (haematology, coagulation, biochemistry, arterial blood gases etc), vital signs (SBP, DBP, heart rate and body temperature), ECG and exposure of MOTREM. The parameters will be listed by treatment group (Placebo, Dose level 1, Dose level 2 and Dose level 3), patient and visit and summarised using standard descriptive statistics. All abnormal values will be identified in patient data listings. Changes from baseline will be described.

PD Analyses: Pharmacodynamic data will be listed by treatment, patient, and visit/time. Summary statistics will be provided by treatment and visit/time. Geometric means and CV will be presented for the primary and secondary PD endpoints.

PD endpoints will be compared between treatments with an ANOVA on logs. Each MOTREM dose group will be compared to placebo with a contract t-test at the 2-sided 10% level.

PK Analyses: Observed MOTREM serum concentrations will be summarised by treatment and corresponding time when sampling occurred. Derived PK parameters will be summarised by treatment.

Clinical Analyses: Several clinical parameters as the clinical events related to sepsis and its complications, the SOFA score total and each sub-score (respiratory, cardiovascular, hepatic, coagulation, renal and neurological system), the vasopressor use, the mechanical ventilation and intubation will be described by treatment group and visit. Standard descriptive statistics will be used.

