15.2 Determination of Sample Size

A formal sample size calculation was not performed for the primary objective of the study. Instead, the sample size 48 patients overall (N=12 for each dose level) was chosen to provide sufficient data for this pilot study of MOTREM in patients with septic shock. This is in line with recommendations for sample size of pilot studies (23).

As this is an exploratory study no adjustments for multiplicity will be employed.

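### The synopsis puts vital signs, a primary safety parameter, behind an omnibus test and Bonferroni, which contradicts section 15.2 and gives up power to detect harm

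*Combined protocol and SAP*

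**What the plan says.** Section 15.1.3 defines the primary endpoint: "Safety and tolerability will be the primary endpoint and it will be monitored during the course of the study as specified below". The first parameter listed under it is "Vital signs: systolic (SBP) and diastolic (DBP) blood pressure, heart rate, and body temperature".

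The only inferential sentence that names vital signs is in the synopsis, under Statistical Methods: "Cytokine distribution and vital signs over time are analysed by a repeated measures ANOVA (mixed models), if significant followed by the Bonferroni post-hoc test". It does not say which model term must be significant or how many comparisons the correction covers.

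The body of the protocol reads differently in four places:

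- Section 15.2: "As this is an exploratory study no adjustments for multiplicity will be employed".
- Section 15.1.1 (and the synopsis itself) has a general rule with no gate: "Between groups comparisons are calculated using an independent t-test or ANOVA-test for quantitative variables with a parametric distribution", with rank tests otherwise. The level is set by "Unless otherwise specified, all treatment comparisons will be two-sided and significance will be assessed at the 5% level".
- Section 15.1.5 has safety parameters, vital signs included, listed by group, patient and visit and "summarised using standard descriptive statistics. All abnormal values will be identified in patient data listings. Changes from baseline will be described". It specifies no between-group difference or interval for them.
- Section 15.1.5 gives pharmacodynamic endpoints, which 15.1.3 labels exploratory, a direct comparison: "Each MOTREM dose group will be compared to placebo with a contract t-test at the 2-sided 10% level" (presumably a contrast t-test). No prior omnibus test or correction is stated.

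**The concern.** There are two problems.

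The first is consistency. The synopsis prescribes a Bonferroni step that section 15.2 excludes. Two analysts could each follow the document and report different inferential results for the same safety parameter.

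The second is direction. An omnibus gate followed by a multiplicity correction protects against false positives. For blood pressure, heart rate and temperature in septic shock, the more costly error is to miss a harmful shift. Read literally, the plan asks more evidence of a primary safety parameter than section 15.1.5 asks of an exploratory biomarker. If the omnibus test is not significant, the synopsis rule produces no dose-placebo comparison, so the reader is not shown how large a harm the data still allow.

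**Working it through.** **1. Patient numbers.** Stage 1 has three cohorts of 3 active and 1 placebo. Stage 2 has 9 per arm (section 15.3). Each dose: 3 + 9 = 12. Placebo: 3 × 1 + 9 = 12. Total: 4 × 12 = 48, which agrees with section 15.2. The documents give no power, effect size, SD or within-patient correlation, so nothing further can be reproduced.

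**2. Assumptions.**
- Normal data and five complete readings per patient. This is favourable: under section 11.3.3 the assessments end with the infusion if it stops before day 5, and under 15.1.1 missing values are not replaced.
- Equal correlation ρ between readings: 0.5, with a range of 0.3 to 0.9.
- The gate is the treatment effect at 5%. A gate on time or on treatment-by-time would behave differently and is not computed here.
- Bonferroni covers 3 comparisons (dose-placebo pairs) or 6 (all pairs).

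**3. Scale.** In units of the single-reading SD, the SD of a five-reading mean is s = √((1 + 4ρ)/5).
- At ρ = 0.5, s = √(3/5) = 0.775.
- A shift of Δ single-reading SD is d = Δ/s SD of the patient mean: 0.5/0.775 = 0.645 and 0.8/0.775 = 1.03.
- For Δ = 0.8, d runs from 1.21 (ρ = 0.3) to 0.83 (ρ = 0.9).

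**4. The two rules compared.** A four-group analysis of patient means was simulated with 48 − 4 = 44 error degrees of freedom. The gated rule needs the F test significant at 5% and then the top-dose contrast at 0.05/3 or 0.05/6. The ungated rule tests the contrast at 5%. At ρ = 0.5, chance of flagging top dose against placebo:

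| Top-dose shift (single-reading SD) | Gated, 6 comparisons | Gated, 3 comparisons | Ungated 5% | Loss (points) |
|---|---|---|---|---|
| 0.5 | 13% | 17% | 34% | 34 − 17 = 17 to 34 − 13 = 21 |
| 0.8 | 41% | 50% | 70% | 70 − 50 = 20 to 70 − 41 = 29 |

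**5. Range over the size of the shift.** In SD of the patient mean, so that any ρ can be read off using step 3. The gated range covers 3 or 6 comparisons and three patterns (top dose only, all doses equal, linear trend):

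| Shift d | Gated | Ungated 5% |
|---|---|---|
| 0.5 | 7–9% | 22% |
| 0.8 | 22–28% | 48% |
| 1.0 | 38–47% | 67% |
| 1.2 | 57–66% | 82% |
| 1.5 | 81–87% | 95% |

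The 50% point is d = 1.03–1.13 for the gated rule and about 0.82 for the ungated contrast. At ρ = 0.5 these are 1.03 × 0.775 = 0.80 to 1.13 × 0.775 = 0.88, and 0.82 × 0.775 = 0.64, in single-reading SD. With 9 per group the gated 50% point rises to d = 1.21–1.32.

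**6. Width of the proposed interval.** The 95% half-width is t(0.975; 44) × s × √(2/12) = 2.015 × 0.408 × s = 0.82s. This gives ±0.64 SD at ρ = 0.5, ±0.55 at ρ = 0.3 (s = 0.663) and ±0.72 at ρ = 0.7 (s = 0.872), before any gain from baseline adjustment.

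**The case against.** The strongest reply is that detection of harm does not depend on this test. Vital signs are listed and summarised by group and visit, with changes from baseline and every abnormal value identified. Clinically relevant deteriorations become adverse events (section 13.3), and treatment-emergent events are tabulated by group. Vasopressor use and sepsis-related events, including hypotension, are described by group. A reader could build rough intervals from the planned means and SDs. The study is an exploratory pilot, and section 15 leaves detail to a separate SAP.

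Much of this stands. A reader might infer that the gated test is the only way vital signs are compared. The documents do not support that, because section 15.1.1 allows ungated tests and 15.1.5 reports fully at the descriptive level. It is also fair that low power here is partly a matter of sample size: at 0.5 SD even the ungated contrast misses about two shifts in three (100 − 34 = 66%).

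Two things are left. Descriptive tables do not state a dose-placebo difference with its uncertainty, and leaving readers to derive one is not a plan. And the loss in step 4 comes on top of the sample-size limit, since both rules use the same 12 per arm. The other safeguards do not supply this estimate: the DSMB reviews blinded data without formal statistical analysis (8.4), and serious hypotension judged unrelated to study drug is exempt from SAE reporting (13.1). Deferral to an SAP explains the missing model term, but not a Bonferroni step that section 15.2 excludes.

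**Conclusion.** The point holds as a contradiction between the synopsis and section 15.2, with differences from 15.1.1 and 15.1.5, and as a poor choice of rule for a safety parameter. Under the stated assumptions (12 per arm, five complete readings, correlation 0.5) the synopsis rule costs roughly 17 to 29 percentage points of detection for a top-dose shift of 0.5 to 0.8 single-reading SD.

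Two stronger readings go too far. A reader might infer that a real haemodynamic harm is more likely missed than found. That depends on the true shift, for which the documents give no figure: for top dose against placebo it is so below about 1.0–1.1 SD of the patient mean and not above, and below about 0.8 SD it is so without the gate as well. A reader might also infer that the sponsor would take a non-significant omnibus test as evidence of safety. No section says this. The plan simply does not guard against it.

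**What to change.** In the synopsis, remove for vital signs the clause that makes comparisons conditional on significance and applies Bonferroni, so that it agrees with section 15.2. Cytokines are named in the same sentence and are also pharmacodynamic endpoints under 15.1.5, so check that part when editing.

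In section 15.1.5, where the clause does not appear, add text along these lines: vital signs will be analysed by a mixed model with treatment, day, treatment-by-day and baseline value; each dose-placebo difference will be reported with an unadjusted 95% confidence interval regardless of any p-value; a non-significant test will not be taken as evidence of no effect. Carry the same wording into the SAP.

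The cost is a wording change and one extra table. The intervals will be wide (step 6). Without correction, the chance of at least one false flag over the three dose-placebo contrasts is about 12% per vital sign at the 5% level (simulated, shared placebo), so some chance differences will need clinical review.
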